- 2) 28 day emergency readmission rates (these are a commonly used indicator within the NHS)
- 3) Time from discharge to next hospital inpatient readmission

Secondary outcomes we will examine include:

- 1) Time from admission to death
- 2) Duration of inpatient admission
- 3) Time from admission to mortality from causes amenable to healthcare
- 4) Time from discharge to admission with ambulatory care sensitive (ACS) conditions
- 5) Time from discharge to next planned admission,
- 6) Overall readmission rates
- 7) Unscheduled readmission rates
- 8) All cause mortality
- 9) International Classification of Diseases 10th Revision chapter-specific mortality
- 10) In-patient costs using Health Resource Group

For those service users with quality of life data we will explore how this changes following involvement of services and how it compares to the measures of quality of life derived from studies within Find and Treat service users and within socially deprived non-homeless groups.

A variety of mortality groupings have been developed to identify causes of death that could be considered avoidable through better medical care depending on age at which they occur. The proposals for the Public Health Outcome Monitoring framework take a similar approach and focus on key areas of avoidable mortality namely: mortality from suicide, communicable diseases, excess

seasonal mortality and, in persons aged less than 75 years, cardiovascular disease, cancer, chronic liver disease and chronic respiratory diseases. All of these are useful indicators within homeless populations.

Sample size:

Our sample size is based upon our estimates of historical data from the two types of SIHHC services (non-clinically led SIHHC services vs. clinically led SIHHC). We estimate that each type will have data from approximately 2,208 individuals for the two-year duration of the study, based on the services seeing on average 92 people per month.

From previous health service evaluation data on homeless groups we expect hospitalisation rates to be 0.7 episodes per person-year for homeless individuals admitted to hospital. An important reduction in readmission rates would be 10%. To undertake a sample size calculation to determine the study size required to detect such a reduction in readmission rates, the following variables were defined:

μ_0 = mean readmission rate in the baseline group = 0.7 episodes per person-year

μ_1 = mean readmission rate in the SIHHC group = 0.6 episodes per person-year

$v=1.96$ =percentage point of the normal distribution corresponding to a 5% two-sided significance level

$u=0.84$ =one-sided percentage point of the normal distribution corresponding to (100%- type II error [FN / (TP + FN)]) at 80% power

Using the following equation we estimated minimum sample size (per group) required for comparison of two rates (readmissions per person-year):

$$\begin{aligned} & (u+v)^2 * (\mu_1 + \mu_0) / (\mu_1 - \mu_0)^2 \\ & (0.84+1.96)^2 *(0.7 + 0.6) / (0.7 - 0.6)^2 \\ & =1019 \text{ person-years per group} \end{aligned}$$

Adjustment for confounders as far as is possible within the analysis results in a doubling of sample size (additional 10% per confounder; likely 10 confounding variables). Therefore 2038 person-years are required per group. Assuming that the SIHHC clinically led and non-clinically led sites see on average 90 service users each month during the study period (which for the purposes of this calculation we have assumed this to be November 2013-November 2015 as many services may have been shut down before this time period and in some we may collect data at an earlier point) we estimate that this translates to a total 2,160 individuals at each of these two types of service.

Follow up: For the primary analysis, individuals will enter the cohort on date of first hospital admission (earliest November 2008) and will be censored at the end of the study period (November 2016) or death, whichever ever comes first.

Confounding variables: As this is a virtual cohort, we will not be able to collect a complete set of confounding variable data on individuals at entry to the study. Where data is provided by SIHHC services we will include age (year and month only), sex. As a result of the lack of baseline data will use historical HES data to determine past medical history from the age of 18 which will be used to create a variable to control for co-morbid conditions and historical hospital usage. Analyses will therefore control for age, gender, comorbidities (identified from HES data) and reason for admission, classified by Healthcare Resource Group (HRGs – groupings of treatment episodes which are similar in resource use and clinical response). Subgroup analyses will compare the different types of SIHCC services. Where provided by the SIHHC services, we will also control in subgroup analysis for medical symptoms, past use of health and social care services, mental health services, smoking, alcohol, and drug taking history, prison and homeless history, employment history.

Health Economics Analysis:

This analysis will cover three economic models. The primary analysis will be a cost effectiveness model (linked to effectiveness data described in the comparative effectiveness section). This model will take an NHS perspective, with costs based on the linked HES data analysis and outcomes based on morbidity and mortality data. Outcomes of homeless users of the two types of SIHHC service (clinically led and non-clinically led) will be compared to each other and homeless controls. Outcomes used for this analysis will include: 1. Overall hospital readmission rates; 2. Unscheduled readmission rates; 3. 28-day emergency readmission rates. Cost estimates will be calculated using national NHS

tariff data, and will include length of hospital stay, emergency admissions, and fixed and variable costs estimates for each of the SIHHC services.

A second cost utility analysis will also be performed. This model will also take an NHS perspective and use costs based on HES data as for the cost effectiveness model, but additionally will use outcomes based on QALY data (primary EQ5D data collected through the field work in a subgroup of SIHHC users at baseline and three month follow up). Data from the two types of service will also be compared to each other and homeless controls from a wider London based survey of 455 homeless individuals accessing Find and Treat screening service for tuberculosis. QALY loss due to morbidity and mortality averted will be examined. Cost estimates will be based on HES data and calculated at two time points: baseline, including retrospective data up to 3 month prior enrolment in the study, and follow up, including prospective data up to 3 month service follow up. Outcome data (QALY) will be calculated from EQ5D data collected at baseline and 3 month follow up.

Cost and effectiveness estimates to be calculated for one year follow up period after entering the study with simulations to 20 years and costs will be discounted at 3.5% per annum. A sensitivity analysis will be carried out in order to examine uncertainties within the cost effectiveness and utility model to examine the uncertainty within the parameters used.

A third cost utility analysis will also be performed using costs and health outcome (consented) data collected from the 6 case study sites. This model will take an NHS and also a wider public sector perspective (e.g. exploring costs for use of social care, prison, supported housing etc.).

The added value of this third economic analysis would be to estimate the cost utility of hospital discharge services from a larger public sector perspective whilst incorporating contextual information from the realist evaluation into the economic evaluation.

The objective of this economic evaluation will be to:

- Evaluate the effect of SIHHC on access to resources and their attached costs (health and mental health services, drug and alcohol services, social care services, housing situation) and on individual wellbeing, and how effect may vary across schemes in different sites
- Compare the effect of SIHHC on access to resources and individual wellbeing to sites relying on standard provision only (i.e. those that do not have access to SIHHC)
- Evaluate any variation in effect of SIHHC across time (dependent on opportunities for tracking participants over the longer term)

Where feasible, data on access to resources will be collected up to 12-month from discharge. This will allow capturing changes in yearly estimate before and after participating in SIHHC. To determine the effect of the SIHHC we will compare individual service use and health outcome after joining the study (based on 3-month follow-up) with our estimate of their service use had they not participated (one year prior to the enrolment). The specialist schemes will then be compared to the standard schemes which will be assessed in the same way. Cost of care will be estimated multiplying individual-specific health care resource utilization by unit cost using available tariff.

Sample size for economic evaluation:

Data from our 455 controls from Find & Treat provides a mean EQ5D visual analogue scale score of 65 and standard deviation of 25. An important improvement (or worsening) in the EQ5D visual analogue scale (0 to 100) as result of the provision of specialist services to this group would be 10. Using a power of 80% at the 0.05 level of significance (two sided) and a two sample *t* means test it is estimated that a sample size of 100 is required to detect such a change. Based on our previous work it is assumed that of all eligible service users identified, 80% of these will consent to take part in the study, and therefore 126 individuals will need to be approached to achieve this sample size. Therefore, 63 individuals will be approached at each of sites 1-6 (for a total of 378 individuals).

Sensitivity analysis and economic discounting: Cost and effectiveness estimates to be calculated for one year follow up period after entering the study with simulations to 20 years and costs will be discounted at 3.5% per annum. A sensitivity analysis will be carried out in order to examine uncertainties within the cost effectiveness and utility model to examine the uncertainty within the parameters used.

Additional ethical issues

The approach to this analysis takes into account the current political and public climate for approvals and linkage of personal identifiable data. We have therefore developed a two stage approach to our work: Firstly, to ensure a minimal dataset for this analysis we will seek individual consent from individuals using SIHHC services, to link their personal data to HES with appropriate NHS ethics approval; secondly, and to improve the power of the study by including a greater number of individuals, we will apply for approval under Section 251 of the NHS Act 2006 to obtain identifiable service user information from services to achieve linkage from an additional sixteen SIHHC services nationally. Our Section 251 request will comply with the Act by being "in the interests of improving service user care" and because there is no reasonable practicable alternative. The linked dataset will be stored in the Farr Safe Haven, a robust infrastructure certified according to international and national information security standards (ISO/IEC 270001 and NHS IG Toolkit). Data providers will securely upload encrypted identifiable data to a highly secure system. The UCL Identifiable Data Handling Solution (IDHS) has recent experience of gaining such approvals within 1 month of application.

The key principles are that:- Data security will be ensured through the a "Trusted Third Party"/"Safe Haven" model where UCL will provide a secure environment for processing identifiable personal data, where only approved researchers' can gain access to the data and where there are penalties for anyone who abuses personal data Research is needed to improve the health of vulnerable populations.

The main ethical issues are those that relate to the use of personal information without the explicit consent of those from whom the information is derived i.e. the second stage of data linkage proposed within this work. The recent Academy of Medical Sciences Report "A new pathway for the regulation and governance of health research" January 2011 highlights the importance of research use of health and social care data to improve understanding of disease and provision of services but state that "access to service user data for research is currently hampered by a fragmented legal framework, inconsistency in interpretation of the regulations, variable guidance and a lack of clarity among investigators, regulators, service users and the public". Despite these complexities we are confident of both the ethical and legal basis of our proposed research. The robust methodology described uses previously approved principles used by ourselves and other groups to link health and non-health data. We have allocated time within the grant to navigate these complexities and ensure relevant approvals. We also plan to host a number of Patient and Public Involvement (PPI) events to engage the full range of stakeholders in addressing these issues

Safeguarding

Researchers have a legal and moral duty to respect the rights of participants for their participation and data to remain confidential. However, there are some circumstances where a disclosure might be made by a participant, or evidence may come to light of a safeguarding issue. In such circumstances, the researcher may have a legal, professional or moral duty to breach the confidentiality of participants and to inform a third party outside of the research team. In such circumstances, the Chief Investigator will inform the Safeguarding Lead in the local authority and /or the NHS Trust, and the local authority Chief Executive and/or the clinical governance lead/Chief Executive in the NHS Trust or the police. The research team will receive training in safeguarding as part of their induction and will be made aware of these procedures. At the commencement of the fieldwork in each study site we will contact local safeguarding leads to alert them the research is taking place. Study participants will also be made aware on the Information Sheet that there may be limits to confidentiality, and that certain situations would mean that the researcher has a duty to inform a relevant authority outside of the research team.

Patient and Public Involvement (PPI)

In addition to the plans for PPI described in the main proposal, this work package will also include three one day engagement events in each of the Public Health Regions of England (North, Central and South). The events will be designed to look at all aspects of data linkage, the ethical issues that may arise, what would be required of services willing to take part in this study and the potential benefits, for example, improved outcomes data. The events will target PPI stakeholders involved in

all SIHHC hospital discharge schemes across England (including service providers and service users). On completion of the study, three further events will be hosted to feedback the findings of study. These events will be in addition to the initial expert seminar and the local feedback events planned for each fieldwork site in order to give sufficient time to look in depth at 'data linkage' (rather than findings around 'hospital discharge per se').

Stage 4: Dissemination and Outputs

In addition to a full project report for the NIHR's journal series and academic papers in learned journals, we will target key professional journals (e.g. Connect, Nursing Times, Community Care, etc.) and organisational/network newsletters and social media with articles and briefings to promote the project throughout and once findings are completed. The combination of these will bring a comprehensive description of the research and academic credibility to the evidence (i.e. the project report and academic articles) with accessible insights and recommendations targeted at specific audiences. Finally, if the findings support this, we will also produce a commissioner's guide (checklist for practice) in the form of toolkit.

In designing for impact we are aware that passive forms of dissemination do not always promote evidence informed practice. We have secured the expert support of Homeless Link who will provide consultancy and support throughout the life of the project to help us develop work in this area.

Gantt Chart

(24 months)	1-3 Q1	4-6 Q2	7-9 Q3	10-12 Q4	13-15 Q5	16-18 Q6	19-21 Q7	22-24 Q8
Preparation & Ethics								
Literature Review								
WP1 Fieldwork Site 1/2								
WP1 Fieldwork Site 3/4								
WP1 Fieldwork Site 5/6								
WP2 PPI Regional Engagement Events (n=3)								
WP2 Data linkage permissions and collection								
WP2 Set up, cleaning of data, and performing linkage								

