For homeless people, length of stay in hospital is reported to be three times longer than for other service users ([name], Halligan and Boyce, 2012). However, this is often attributed to the complexity of homeless people's presenting health needs (multimorbidity) rather than to delayed discharge. In other words, 'homeless service users' stay three times as long as they are [three] times as sick' ([name] and Halligan, 2010, p306). Despite this, there is strong evidence that a key problem facing homeless people in hospital is 'poor care' which often leads to difficulties accessing appropriate treatment, early 'self-discharge' and being discharged prior to being 'medically fit'. A review of hospital admission and discharge arrangements by Homeless Link (2012) identified 'countless examples' of the mention of homelessness on admission triggering prejudice among hospital staff. According to one homeless interviewee, 'As soon as [the nursing staff] find out you're homeless they want you out of the door' (p7). The review reported that more than 70% of homeless people were 'discharged straight back onto the streets, further damaging their health and all but guaranteeing their readmission' (p6). The main recommendation of the Homeless Link report is for cultural change in the way homeless people are viewed and treated in the NHS.

Other themes highlighted in the Homeless Link review and the literature more broadly include: hospital staff not asking people about their housing situation on admission and not addressing needs relating to drug and alcohol use (e.g. ensuring access to methadone); hospital staff not alerting accommodation providers to the fact that a person is in hospital leading to tenancies being terminated; hospital staff having a poor understanding of the services available to homeless people, including overestimating the level of care that can be provided in hostel settings leading to unsafe discharges; a lack of practical support, such as no replacement of soiled clothing; uncertainty regarding where the involvement of one sector should start and end, including little agreement about how far hospital staff should be expected to proactively seek accommodation; a lack of appropriate accommodation options raising the question of whether 'signposting' is an adequate response if this potentially leads to discharge back onto the streets

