The main focus of the second follow-up interview will be on: (i) Patterns of service use in the intervening three months period, including any readmission to hospital (What support was received? Did the support materialize as planned? Did the support meet self-perceived needs?); (ii) What was liked and disliked about the support? (iii) How was the support perceived to have helped? What goals were achieved? What goals were still aspired to and what additional support might help to achieve those goals?

The timing of the second interview at three months is intended to give sufficient time to reveal potential for continuity (i.e. support beyond the 6-8 weeks cut off point often associated with intermediate care support) but not so far into the future as the connections with the initial hospital and discharge planning episode will likely be lost to memory.

We will also seek homeless people's written consent to access support plans and personal information which may be held by a range of providers.

The inclusion criterion for service users will be that they are experiencing 'multiple exclusion homelessness' (MEH). This criterion is chosen as it encompasses multimorbidity (a range of health issues) and compounding factors potentially impacting on well-being which are linked to experiences of 'deep social exclusion'. People experience MEH if they are 'homeless' (broadly defined, to include temporary/unsuitable accommodation as well as sleeping rough), and have also experienced one or more of the following domains of deep social exclusion –'institutional care' (prison, local authority care, stays in mental health hospitals or wards); 'substance misuse' (drug problems, alcohol problems, abuse of solvents, glue or gas); participation in street culture activities (begging, street drinking, 'survival' shop lifting or sex work) (Fitzpatrick et al. 2011 p.502).

Service users will be recruited on the basis that they are 'key informants' with regard to different experiences of MEH which might highlight different patterns of service user (including barriers). In each site, we will purposively recruit service users referred either to specialist schemes or in (standard care) to discharge coordinators/ward managers. Recruitment will aim to target the following groups/demographics and whenever possible we will approach people in the order to which they referred to the service:

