Stage 3b: Delivery of Work Package Two – Data Linkage and Health Economic Analysis

Overview

The most comprehensive assessment to date of the health care usage of homeless populations in England was prepared and published by the Department of Health in March 2010. The report ‘Healthcare for Single Homeless People’ (Office of the Chief Analyst and Department of Health, 2010) analysed Hospital Episode Statistics data for people who gave their address as “No fixed abode” and also summarised data from six specialist GP practices who provided healthcare to homeless people. Extrapolating from these data they estimated that health care costs of homeless people are approximately eight times greater than those of similarly aged adults and this client group have almost three times the average length of stay when hospitalised with a cost of at least £85 million per year. However, there were several key problems with this analysis: the use of the “No fixed abode” category will miss many homeless people, for example those living in shelters, hostels or other temporary accommodation; the size of denominator populations to allow comparison of hospitalisation rates was highly uncertain and, those using specialist practices may be highly unrepresentative of the homeless population. To address these issues, WP2 will use data on homeless hospital admissions in order to determine the long term outcomes required to investigate the effectiveness and cost-effectiveness of different hospital discharge arrangements in England.

Data sets used for WP2

WP2 will extend the number of research sites to 20. This will include the 6 realist evaluation sites, plus a further 7 sites which have ‘clinically led’ SIHHC and 7 sites which have ‘housing link’ worker (non-clinically led) SIHHC. Appendix One provides a summary of the data which will be collected in each site and how for practical data collection purposes WP1 and WP2 will be integrated on the ground.

A total of five data sources will be used within this linkage study.

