1. **Unconsented data:** SIHHC (hospital discharge projects) taking part in the study (Sites 1-2, 7-13 using clinically led services; Sites 3-4, 14-20 using non-clinically led services) will be asked to provide identifying and demographic data (forename, surname, aliases, date of birth, sex, current or previous postcodes, nationality, ethnicity, NHS number) for service users during the period November 2013 to a maximum of November 2016. However, note that for some services we will collect data that ends before 2016 as some will have been shut down before this time period and in some we may collect data at an earlier point, providing we receive the appropriate permissions and ethical and CAG approvals.
2. **Consented data from a subset of study fieldwork sites (n=6 sites):** We will collect data on 252 individuals across 4 sites with SIHHC (hospital discharge) schemes (two sites that are clinically led (Sites 1&2), two sites that are non-clinically led (Sites 3&4)) and on 126 individuals across two sites with standard /usual care (Sites 5&6), giving 378 individuals in total (63 per site x 6 sites). The data collection for this part of the work is contained in a baseline, exit and 3-month follow up data questionnaire and will collect information on demographic information, along with dates of contact with SIHHC services, past use of health and social care services, mental health services, smoking, alcohol, and drug taking history, prison and homeless history, employment, user satisfaction with service delivery, and data on quality of life (EQ5D). The voluntary sector hospital discharge projects will be asked to help collect this data on behalf of the research team as part of their routine outcomes monitoring and will be reimbursed for doing so at a rate of £20 per completion. The data flow chart shows how this work will be integrated with WP1 for practical purposes.
3. The data flow chart shows how this work will be integrated with WP1 for practical purposes.

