Secure upload of consented (WP2FU) individual data to Farr data safe haven (WP2/FU)

Group B

Data is to be collected for Work Package 2 (Comparative Effectiveness and Economic Evaluation) Only

Homeless service user is on the hospital ward.

Step 1

Seek the support of hospital/scheme discharge coordinators to recruit 53 service users for Group B at each site (n=318)

Step 2

The hospital/scheme discharge coordinator informs the service user about the study, provides an invite letter and a 'Service user Information Leaflet' (Form B). These will be talked through and permission sought to pass the service user's contact details to the research team.

Step 3

A few days after discharge from hospital, the researcher makes contact with the service user to arrange a community visit.

The researcher provides another copy of the 'Service user Information Leaflet' (Form B) answers any questions and if the service user is willing to participate takes informed consent (either written or verbal) (Form B)

Step 4

A baseline questionnaire is completed (WP2/BL)

Step 5

Secure upload of consented (WP2/BL) individual data to Farr data safe haven

Step 6

A follow-up questionnaire is completed on exist from the scheme and at three months follow up (WP2/FU)

Step 7

Secure upload of consented (WP2/FU) individual data to Farr data safe haven (WP2)

Box 3: Arrangements for Data Collection in Fieldwork Sites 7-20*

Scheme Typologies Across Sites 7-20

Sites 7-13: In these sites the hospital has access to a specialist integrated hospital discharge scheme for homeless people which is 'clinically-led'

Sites:14-20 In these sites the hospital has access to a specialist integrated discharge scheme for homeless people which is non-clinical (e.g. provides access to housing advice only)

Comparator Databases:

Find and Treat [comparator database]

Hospital Episode Statistics [comparator database representative sample of lowest quintile of deprivation equal in size to the Find and Treat dataset]

Step 1

CAG Approvals in Place

Step 2

Unique study ID created for each individual record and left on site

Step 3

Secure upload of operational service data (non-consented) to Farr data safe haven

[figure not shown]
Step 4

Transfer of sensitive data (first name, surname, dob, sex, current or previous postcodes, nationality, ethnicity, NHS Number, Hospital of admission, Study ID

Step 5:

Transfer of HES ID and HES data back to Farr data safe haven

Box 4: Detailed Data Flow for WP2:

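### Consented participants are found by different routes at specialist and standard-care sites, so their housing mix may differ, and the specialist-versus-standard comparison is not adjusted for homeless history as written

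*Protocol*

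**What the plan says.** Protocol, Stage 3a, item [3:4], on recruiting interviewees: "we will purposively recruit service users referred either to specialist schemes or in (standard care) to discharge coordinators/ward managers". The inclusion criterion there is multiple exclusion homelessness, with homelessness "broadly defined, to include temporary/unsuitable accommodation as well as sleeping rough", plus at least one further domain of exclusion.

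Appendix One, Box 2, covers the whole consented sample. Group A (10 per site) is filled by age and sex quota, and later service users go to Group B (53 per site). Both groups depend on the same kind of gatekeeper; for Group B: "Seek the support of hospital/scheme discharge coordinators to recruit 53 service users for Group B at each site". Box 2 does not restate the multiple exclusion criterion for Group B.

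Data sets used for WP2, item 2, adds: "The voluntary sector hospital discharge projects will be asked to help collect this data on behalf of the research team". Sites 5 and 6 have no such project. The same item lists homeless, prison, and drug and alcohol history among the questionnaire data for all six sites.

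Confounding variables names age, gender, comorbidities and reason for admission as the main adjustment set. Homeless history enters only in subgroup analysis, and only where specialist (SIHHC) services provide it.

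Health Economics Analysis, third cost-utility analysis, compares each person with an estimate from their own prior year, and then: "The specialist schemes will then be compared to the standard schemes which will be assessed in the same way". No covariates are named.

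**The concern.** This comparison is not randomised, and the way people are found is part of what separates the groups. At Sites 1-4 a homelessness service has already identified and accepted the patient. At Sites 5-6 the patient must first be recognised as homeless by general hospital staff.

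The protocol gives reason to expect uneven recognition. Its literature summary lists "hospital staff not asking people about their housing situation on admission" among the known failings. In the WP2 overview it faults the hospital-record address category for no fixed abode because it "will miss many homeless people, for example those living in shelters, hostels or other temporary accommodation". If recognition depends on housing type, two samples that both meet a broad definition of homelessness can hold different proportions of rough sleepers, hostel residents and people in temporary accommodation.

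At stake are the EQ5D comparison of specialist with standard sites and the third economic analysis. A difference in housing mix, with its own course of health and service use, could be read as an effect of the scheme or could hide one. A recruitment difference cannot be undone later, and adjustment can correct only for what was measured.

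**Working it through.** **1. Does the route differ, and for whom?** The sentence in [3:4] governs the interviewees: 10 × 6 = 60. Box 2 carries the gatekeeper arrangement to Group B: 53 × 6 = 318. Together 60 + 318 = 378, the full consented sample. The coordinator belongs to the scheme or to the hospital, depending on the site.

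**2. Is there a common filter?** Partly. The [3:4] criterion applies at every site but spans rough sleeping to temporary accommodation, acts only on people already identified, and is not restated for Group B. The Group A quotas fix age and sex, not housing.

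**3. Is the difference handled in analysis?** Homeless history supplied by specialist services exists only for sites that have one, so that rule cannot adjust a contrast with Sites 5-6. The six-site questionnaire could, but the third economic analysis does not say it will be used.

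**4. The plan's own sample size.** Inputs from Sample size for economic evaluation: SD 25, difference 10, two-sided 0.05, power 80%, consent 80%.

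- n per group = 2 × (1.96 + 0.84)² × 25² / 10² = 98.0. Unrounded percentiles give 98.1, so 99. The t-test version gives 99.08, so 100, as stated.
- 100 / 0.80 = 125, against 126 = 2 × 63 stated. 6 × 63 = 378.

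The figure reproduces. Size is not the problem: a larger sample would not remove a selection difference.

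**5. Illustration only, for a raw follow-up contrast.** Let d be the difference between samples in the share of one housing type, and g the gap in mean EQ5D visual analogue score between housing types. The unadjusted bias is B = d × g. The documents give neither d nor g, so both are assumptions: d from 0.10 to 0.50, g from 5 to 20 points.

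SE with 100 per group = 25 × √(2/100) = 3.54. With all four specialist sites pooled at 80% consent (about 202 against 101), SE = 25 × √(1/201.6 + 1/100.8) = 3.05. The false-positive rate with no true effect is P(|Z + B/SE| > 1.96).

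| d | g | B | Rate, 100 v 100 | Rate, 202 v 101 |
|---|---|---|---|---|
| 0.10 | 5 | 0.5 | 5.2% | 5.3% |
| 0.20 | 10 | 2.0 | 8.7% | 10.1% |
| 0.30 | 10 | 3.0 | 13.6% | 16.6% |
| 0.20 | 20 | 4.0 | 20.5% | 25.9% |
| 0.50 | 20 | 10.0 | 80.7% | 90.6% |

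If the bias runs against the schemes, it costs power instead: at B = 3 with 100 per group, power for a true 10-point gain is Φ((10 − 3)/3.54 − 1.96) = 51%.

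**6. Effect of the before-after design.** For change from baseline, the bias becomes d × (g at follow-up − g at baseline). It is zero if the gap between housing types is constant, and remains if they follow different courses. The table is therefore not an estimate for the planned change comparison.

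**The case against.** The strongest reply is that the protocol already does much of what is needed. It states one inclusion criterion for interviewees at all sites, sets identical Group A quotas, approaches people in referral order where it can, and uses the same recruitment steps at all six sites. The third economic analysis starts from each person's own prior year. The Site Selection text says the qualitative phase is not meant to compare scheme types directly. Covariates for an economic model are often left to a statistical analysis plan, which is not shown here. The primary economic analysis uses linked hospital data and is untouched.

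Much of this stands. The shared criterion and the before-after step should reduce any bias, and the disclaimer is fair for the 60 interviews. It does not cover the quantitative comparison of specialist with standard sites. A later plan may add covariates, so the differing recruitment source is the firmer half of this point.

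A reader might infer that the standard-care sample will hold more rough sleepers and so flatter the schemes. The documents do not support that direction. Sites 1 and 2 are expected in inner London and an inner city, and the GP-led Pathway model is described as supporting emergency staff with frequent attenders, so the specialist samples could be the more complex. The remark about staff not asking comes from a national review and does not describe Sites 5 and 6. Site 5 is chosen because it has a discharge protocol.

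**Conclusion.** The concern holds in a limited form. Recruitment source is confounded with site type across the consented sample, the protocol's own background makes uneven identification plausible (most clearly at Site 6), and the specialist-versus-standard EQ5D and cost comparison is, as written, not adjusted for homeless history.

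The documents do not show that the groups will differ in housing mix, in which direction, or by how much. Nor would it be right to say that no control for housing is planned anywhere: homeless history appears in the subgroup rule, but in a form that cannot serve this contrast. The range of 0.5 to 10 points rests entirely on assumed inputs and on a raw follow-up contrast, so it shows that the issue can matter against a 10-point target and nothing more.

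The reach is the EQ5D comparison and the third economic analysis. The correction is cheap and the recruitment part has to be made before enrolment, so it should be made.

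**What to change.** 1. In Health Economics Analysis, state that the specialist-versus-standard EQ5D and cost comparisons will be adjusted for baseline EQ5D and for the homeless, prison, and drug and alcohol history in the six-site baseline questionnaire. Rely on that questionnaire: the detailed list of nights by housing type in Appendix One, Box 5, is a list of variables that services might hold, and the protocol expects few sites to have all of them. Box 2 has the baseline questionnaire completed after discharge, so baseline EQ5D may already carry some effect of in-hospital support; show results with and without it.
2. In Appendix One, Box 2, apply the [3:4] eligibility criterion to Group B, ask the same housing question at all six sites, approach eligible people in order of referral, and log by site those identified, approached and consented.

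There is no need to enrol patients at Sites 1-4 whom the scheme has not taken on. That would change the question from use of a scheme, which the research design section sets out to study, to availability of one.

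Cost: the first change uses data already planned. The second adds a little recruitment paperwork. Some selection will remain, because people never recognised as homeless cannot be logged or adjusted for, and the report should say so.
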